2.3. Pooling Algorithm for Analysis Centers

The data from all investigative sites will be pooled for all analyses.

2.4. Analysis Sets

2.4.1. Efficacy Analysis Set(s)

The all-treated population is defined as all subjects who have received at least 1 dose of study drugs (either ibrutinib or nivolumab).

The response-evaluable population is defined as all subjects who receive at least 1 dose of both study drugs (ibrutinib and nivolumab), and have a pretreatment, and at least 1 posttreatment disease assessment; unless no post-baseline scan was performed due to AE possibly related to treatment or clinical progression or death.

ORR, DOR, DOSD, PFS and OS will be analyzed using the all-treated population. In addition, ORR will also be analyzed based on response-evaluable, if deemed necessary.

DOR will be analyzed for subjects who achieve a partial response [PR (+L)] or better. DOSD will be analyzed for subjects who achieve a stable disease (SD) or better.

2.4.2. Safety Analysis Set

The safety population is defined as all subjects who receive at least 1 dose of study drug, which is same definition as the all-treated population.

2.4.3. Pharmacokinetics/Pharmacodynamic (PK/PD) Analysis Set

This population consists of all subjects who receive at least 1 dose of study drug (either ibrutinib or nivolumab) and have at least 1 posttreatment sample collected during treatment to determine the concentration or pharmacodynamic biomarker response.

2.5. Definition of Subgroups

Exploratory subgroup analyses will be performed for the primary efficacy endpoint.

- Age (<65 vs. ≥65 years)
- Sex (male vs. female)
- Race (Caucasian vs. Other)
- Prior lines of therapy (1 vs 2 to 4 vs >4)
- Baseline Eastern Cooperative Oncology Group (ECOG) performance status (0 and 1 vs 2)
- Region (United States vs. Non-United States)

- SLL vs Non-SLL
- Transformed DLBCL vs Non-transformed DLBCL

2.6. Imputation of Missing Dates

In general, missing date of initial diagnosis, date of death and start and end dates of AE, prior, concomitant and subsequent therapies will be imputed according to the following rules:

- General rules
 - If date is completely missing or year is missing, no imputation will be made.
 - If only year is present but month and day are missing, then June 30th will be used.
 - If only day is missing but year and month are available, then the 15th of the month will be used
- Start and end dates rules
 - Start date will be imputed before end date
 - If end date is not missing (i.e., not imputed) and before the imputed start date, then end date will be used
 - If end month and year are not missing and before imputed start month and year, then end month and year will be used
 - If imputed end date is before start date, then start date will be used

However, the above imputation will be modified by the following rules sequentially:

- For death: if the imputed date is before the last date that the subject is known to be alive, the latter date + 1 day will be used.
- If any imputed date is after date of death, then date of death will be used
- For initial diagnosis and prior therapies: if imputed date is on or after the first dose date, then first dose date - 1 will be used.
- For AE and concomitant medications: The imputed start date will be adjusted sequentially using the following steps
 - If it is in the same month and year but before the first dose date, then the first dose date will be used, or if it is in the same month and year but after the last dose date + 30 days, then the last dose date + 30 days will be used
 - If the end date is not missing and the imputed start date is after the end date, then the end date will be used.

- If the imputed start date and is after date of death, then date of death will be used.
- If it is in the same month and year but after the 1st subsequent systemic therapy start date, then the 1st subsequent therapy start date will be used.
- For subsequent therapies: if imputed date is before the treatment discontinuation date, then the treatment discontinuation date will be used.

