| 
Treatment Period begins with the first administration of study therapy. EOT visit is required for all subjects and should take place within 30 days after last dose of study therapy with a window of ±7 days. If the subject requires subsequent anti-lymphoma/neoplastic therapy in the interim period between last dose of study drug and the EOT visit, then this visit should be completed just prior to initiation of subsequent therapy. Follow-up visits in all subjects will be completed every 3 months with a window of ±7 days until death or end of study. Note that the first FU visit should be approximately 100 days after end of nivolumab therapy; during this first FU visit, additional sampling will be done.
 
After the clinical cutoff, subjects who are ongoing on treatment continue all assessment per protocol, however data collected on eCRF will be limited to at least: SAEs and AEs Grade ≥3, laboratory assessments (Grade ≥3 or clinically significant), efficacy assessments, survival status, and study treatment administration.
 
Per Amendment 7, subjects who are receiving study treatment will continue all assessments per protocol. Data collected in the eCRF will be further limited to: SAEs and Grade ≥3 AEs that are at least possibly related to treatment, AEs leading to discontinuation or modification, efficacy assessments, and study treatment administration.
 | | | | | | |
| Weight/Height | Height at Screening only. | X | X | X | X | |
| 12-lead ECG | Assessment of triplicate ECG to determine QTcF; repeat ECG 3 times approximately 1-2 minutes apart. Predose Baseline= prior to any study treatment Predose C2D1=within 1 hour prior to nivolumab dosing | X | •Predose •Immediately after nivolumab infusion on C1D1 •2 hours after ibrutinib dosing on C1D1 | •Cycle 2 Day1: predose •Cycle 5 Day 1: after end of nivolumab infusion •To be repeated as clinically indicated | X | |
| Concomitant Medications | Collect up to EOT (within 30 days after the last dose of ibrutinib or whichever treatment occurred last). Thereafter, collect only subsequent anti-lymphoma/neoplastic therapy. | <-----X-----> | | | | |
| Adverse Events | Record all AEs from signing of ICF to EOT (within 30 days after the last dose of ibrutinib or nivolumab, whichever treatment occurred last). | <-----X-----> | | | | |
| Laboratory Assessments | | | | | | |

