5.1. Adverse Events

The verbatim terms used in the CRF by investigators to identify adverse events will be coded using the current Medical Dictionary for Regulatory Activities (MedDRA). The severity of adverse events is assessed in NCI common toxicity criteria for adverse events (CTCAE) Version 4.03.

Treatment-emergent adverse events are 1) adverse events that occur after the first dose of study treatment, and up to + 30 days after last ibrutinib or up to 100 days after last dose of nivolumab whichever is last, or the start date of a subsequent systemic anticancer therapy, whichever is earlier (including both dates), 2) any adverse event that is considered study treatment - related (at least relationship to one drug of combination will be considered related) (i.e., possibly, probably, or very likely related to study drug) regardless of the start date of the event, 3) any adverse event that is present at baseline but worsens in severity and is subsequently considered drug-related by the investigator.

Treatment-emergent adverse events will be summarized by system organ class (SOC) and preferred term (PT), by severity, by relationship to study treatment, and by action taken. For each adverse event, the percentage of subjects who experience at least 1 occurrence of the given event will be summarized. Tables will be sorted by frequency in incidence (from the highest to lowest incidence). The same summary will be provided for drug-related adverse events, serious adverse events, and drug-related serious adverse events, immune-related events as well as adverse events leading to treatment discontinuation, and death.

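### The SAP's same-month condition never corrects an adverse event start known only to the year, so for July to December starters such events in the first-dose year fall before treatment and, if not drug-related, leave the treatment-emergent summaries

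*SAP*

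**What the plan says.** SAP 2.6 gives two general imputation rules for partial dates:

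- Year only: "If only year is present but month and day are missing, then June 30th will be used".
- Month and year: "If only day is missing but year and month are available, then the 15th of the month will be used".

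Imputed AE start dates are then adjusted in sequence. The only step that moves one forward is "If it is in the same month and year but before the first dose date, then the first dose date will be used". Its mirror image on the late side is also limited to the same month and year, and pulls a date back to last dose + 30 days. The remaining steps can only move a start earlier. One is "If the end date is not missing and the imputed start date is after the end date, then the end date will be used"; the others cap it at death or, within the same month and year, at the start of subsequent systemic therapy.

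SAP 5.1 then defines treatment-emergent AEs (TEAEs) by three limbs:

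1. A date limb: "adverse events that occur after the first dose of study treatment, and up to + 30 days after last ibrutinib" or 100 days after last nivolumab, whichever is last, cut short by subsequent systemic anticancer therapy.
2. A relatedness limb, which keeps any AE at least possibly related to either drug "regardless of the start date of the event".
3. A limb for baseline AEs that worsen and are then considered drug-related.

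Protocol Table 1 says of collection: "Record all AEs from signing of ICF to EOT". SAP 2.2 allows up to 28 days of screening before first treatment.

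**The concern.** The same-month condition suits a date with only the day missing: the 15th may fall a few days before first dose, and the rule repairs that. It does not suit a date with only the year known, where 30 June may lie months before first dose and nothing brings it forward.

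The result is a start date that the known information does not support and that can be impossible under the collection rules. An AE that may have begun on treatment then fails the date limb of the TEAE definition. This is a single-arm combination study, so the all-causality safety tables have no control group to set against them. They should not depend on the calendar month in which a subject was first dosed.

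The neighbouring rules in SAP 2.6 for prior and subsequent therapies compare the imputed date with the reference date without any same-month condition.

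**Working it through.** The plan states no figure on this point. The check applies SAP 2.6 and 5.1 literally to every possible first-dose date D in a calendar year, for an AE known only to that year. The imputed start is I = 30 June.

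**1. Can the forward correction fire?** It needs month(I) = month(D) and I < D. If D is in June, D is at most 30 June, so I < D is false. In any other month the first condition fails. It fires on 0 dates.

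**2. How many dates leave the AE before treatment?** All D from 1 July to 31 December: 31 + 31 + 30 + 31 + 30 + 31 = 184. As a share, 184/365 = 50.4% or 184/366 = 50.3%.

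**3. When is the imputed date impossible?** The earliest screening day is D − 28.

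- D = 28 July gives 30 June, which is just possible.
- D = 29 July gives 1 July, which is after I. From this date on, I precedes any possible screening day.
- D = 15 September puts I 77 days before first dose, and 77 − 28 = 49 days before the earliest screening day.

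**4. Where does the problem not arise?**

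- An AE dated to the year after first dose: 0 placed before treatment.
- An AE known to the month of first dose (imputed to the 15th): 0 left uncorrected.

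**5. What happens to an affected AE under SAP 5.1?**

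| Investigator's attribution | Date limb | Relatedness limb | Result |
|---|---|---|---|
| Not related or doubtful | fails | fails | not a TEAE |
| At least possibly related | fails | met | TEAE |

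The loss is therefore confined to AEs not judged drug-related. They leave the all-causality TEAE, serious AE, and discontinuation and death summaries, reading these as built on the same treatment-emergent set.

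**6. Dates are not events.** Assume even first doses over the year and a constant AE rate, with time in fractions of a year. Among AEs that truly fall in the TEAE window and in the first-dose year, the share from July to December starters is:

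- Window running to year-end: (0.5²/2)/0.5 = 0.125/0.5 = 25%.
- Window of 60 + 100 = 160 days (the 2 months of therapy that SAP 1.2 expects in DLBCL, nivolumab given to the end): w = 160/365.25 = 0.438. All starters: w(1 − w) + w²/2 = 0.342. July to December starters: w(0.5 − w) + w²/2 = 0.123. Share 0.123/0.342 = 36%.

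Both shares are before drug-related AEs are taken out.

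**7. Late side.** Suppose both drugs stop on 15 January. The SAP 5.1 window ends about 25 April (+100 days). A year-only AE goes to 30 June, outside the window. The correction looks to 14 February (+30 days), a different month, and does not fire.

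The 30-day reference can also matter when the month is known. If both drugs stop on 5 March, the window ends on 13 June (26 + 30 + 31 + 13 = 100 days). An AE known only to June goes to the 15th, two days outside. Last dose + 30 is 4 April, so again nothing fires. Both examples assume no known end date, death or subsequent therapy that would change the result.

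**8. With the fix.** If a year-only date in the first-dose year that falls before D is set to D, the count in step 2 becomes 0.

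**The case against.** The strongest reply is that very little is lost. AEs are collected prospectively at visits in each 14-day cycle, and incomplete entries can be queried (Protocol 18.5), so year-only starts should be rare. Neither document says how many there are. The primary endpoint does not use these dates. This stands, and it makes the point a minor one.

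Four stronger readings are tempting, and the documents do not support them.

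- **That all such AEs are dropped.** The relatedness limb of SAP 5.1 keeps any AE at least possibly related to either drug, so the drug-related summaries do not lose events this way. The AE's known year must also be the year of first dose.
- **That the error always lowers the count.** AEs are recorded from consent. Take a subject first dosed in March with a February screening AE known only to the year. It goes to 30 June and counts as emergent if still in the window, unless a known end date pulls it back. The imputation errs in both directions.
- **That half of subjects or events are affected.** Half describes first-dose dates only. Under the simple assumptions above, the share of relevant events is 25% to 36% before attribution is considered, and it applies only to year-only dates.
- **That nothing else limits the late side.** The end-date and death rules carry no same-month condition and will bring some late dates back.

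Some affected AEs will also truly have begun before treatment. The same adjustment covers concomitant medications, but SAP 3.6 states no date-based exclusion for them, so no consequence is shown there.

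None of this makes the rule right. It is a stated rule that gives a wrong date, not a detail left open.

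**Conclusion.** The point holds as a minor defect in a date rule. For first doses from 1 July to 31 December (184 of 365 or 366 dates), SAP 2.6 places a year-only AE from the first-dose year before treatment. For first doses from 29 July, the imputed date precedes any possible screening day. Only AEs judged not related or doubtful are lost, and only from the all-causality summaries. The late-side correction has the same limit, subject to the end-date and death rules, and its 30-day reference disagrees with the 30/100-day window in SAP 5.1.

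The date mechanics need no assumption beyond the SAP text and the 28-day screening limit. The number of events lost cannot be computed, because the documents give no count of year-only dates; it is probably small. The overall response rate is not affected.

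**What to change.** Amend the AE start-date steps in SAP 2.6 in two places.

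- **Early side.** Compare only the known parts of the start date with first dose. If they match (same year, or same month and year) and the imputed date is earlier, use the first dose date, unless a known end date shows that the AE ended before first dose. The existing end-date step already supports that exception.
- **Late side.** If the known parts are compatible with the SAP 5.1 window and the imputed date is later than its end, use the window end as SAP 5.1 defines it: ibrutinib + 30 or nivolumab + 100 days, whichever is last, or the start of subsequent systemic therapy if earlier. This replaces last dose + 30 days.

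State also that an AE dated to the day of first dose counts as emergent, since both the existing correction and this one depend on it.

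The cost is about two sentences in the SAP and the matching conditions in the program, with no new data. The downside is that some AEs that truly began before treatment will be counted as emergent. A count of AEs with imputed start dates beside the TEAE tables would show how much depends on the rule.

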2.7. Other General Definitions

Year and Month

1 year = 365.25 days and 1 month = 30.4375 days.

Age

Use Age (year) collected in the case report form (CRF), which is the number of integer years from the date of birth to the date of informed consent.

Date of overall response for each time point

Date of assessment at that time point. When different assessments for the time point are performed on different dates, the date of overall response is the date of the last assessment performed when the responses PR(+L) or better [except for biopsies - biopsies of tumor or suspected tumors (such as lymph nodes/nodal masses) or extranodal masses (such as GI biopsy, skin lesions, etc.), cytology assessments], or the date of earliest assessment showing progression when the response is PD or relapse from CR.

Date of response

Date of first observed response [PR(+L) or better]. For CLL patients, time to response is calculated from onset of PRL.

Date of best response

Date of first observed best response [PR(+L) or better]. For instance, for subjects who achieved PR followed by CR, PR will be the initial response and CR will be the best response (the date of evaluation with first time CR is reported is the date of best response). Use the ranking below to choose the best response. The response corresponds to the lowest rank of number is the best response:

Rank	Response
1	CR
2	CRI
3	PR
4	NPR
5	PR WITH LYMPH (PRL)

6	SD or no response
7	PD
8	NE
10	UNK
11	(missing)

Date of progression

Date of first observed progression.

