Attachment 6.1: International Workshop on Chronic Lymphocytic Leukemia (IWCLL)

The International Workshop on Chronic Lymphocytic Leukemia (IWCLL) recommendations for the management of CLL in clinical studies and general practice are presented below (Hallek 2008)²³.

| Response Category | Definition |
|---------------------------------|--|
| Complete Response (CR) | 
Group A^{1,2}
 
 • Lymphadenopathy^a: none >1.5cm • Hepatomegaly: none • Splenomegaly: none • Blood lymphocytes: <4000/μL • Marrow^c: Normocellular, <30% lymphocytes, no B-lymphoid nodules. Hypocellular marrow defines CRi 
Group B^{1,2}
 
 • Platelet count: >100,000/μL • Hemoglobin>11 g/dL • Neutrophils^c: >1500/μL 
Complete Response with an Incomplete Marrow Recovery (CRi) is defined as a complete response with an incomplete recovery of the subject's bone marrow. Subjects who have a CRi fulfill the criteria for a CR, but continue to have persistent anemia, thrombocytopenia, or neutropenia, and a hypocellular bone marrow. These cytopenias are due to drug toxicity in the bone marrow and are not due to any evidence of CLL.
 |
| Partial Response (PR) | 
Group A^{1,3}
 
 • Lymphadenopathy^a: Decrease \geq50% • Hepatomegaly: Decrease \geq50% • Splenomegaly: Decrease \geq50% • Blood lymphocytes: Decrease \geq50% from baseline • Marrow^c: 50% reduction in marrow infiltrates or B lymphoid nodules 
Group B^{1,3}
 
 • Platelet count: >100,000/μL or increase \geq50% over baseline • Hemoglobin: >11g/dL or increase \geq50% over baseline • Neutrophils^c: >1500/μL or increase \geq50% over baseline 
Nodular Partial Response (nPR) nPR is a response where subjects meet the criteria for a CR, but the bone marrow biopsy shows that there are still B-lymphoid nodules present. These nodules are residual disease and therefore the subject is termed an nPR.
 
Partial Response (PR) with Lymphocytosis PR with lymphocytosis is a response where subjects meet the criteria for a PR and have persistent lymphocytosis.
 |
| Stable Disease (SD) | Not meeting criteria for CR, CRi, nPR, PR, or PD |
| Progressive Disease (PD) | 
Group A^{1,4}
 
 • Lymphadenopathy^a: increase \geq50% or appearance of new lesions >1.5 cm |

| Response Category | Definition |
|-------------------|--|

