| | 
 • Hepatomegaly: increase $\geq 50\%$ or appearance of new hepatomegaly • Splenomegaly: increase $\geq 50\%$ or appearance of new splenomegaly • Blood lymphocytes • Marrow^c: increase $\geq 50\%$ over baseline^d 
Group B^{1, 4}
 
 • Platelet count: Decrease of $\geq 50\%$ from baseline secondary to CLL • Hemoglobin: Decrease of $> 2\text{g/dL}$ from baseline secondary to CLL • Neutrophils^c |
| Other | 
Treatment-related Lymphocytosis
 
Treatment-related lymphocytosis is defined as an elevation in blood lymphocyte count of $\geq 50\%$ compared with baseline that occurs in the setting of unequivocal improvement in at least 1 other disease-related parameter, including lymph node size, spleen size, hematologic parameters (hemoglobin and platelet count), or disease-related symptoms. Treatment-related lymphocytosis is isolated lymphocytosis occurring when no other criteria for progressive disease are met. In this particular setting, it will not be considered PD.
 |

^a. Sum of the products of multiple lymph nodes (as evaluated by CT scans).

^b. Defined as a decrease in lymph nodes of $\geq 50\%$ either in the sum products of the diameter of up to 6 lymph nodes, or in the largest diameter of the enlarged lymph node detected prior to the therapy, as well as no increase in any lymph node and no new enlarged lymph nodes. Note: in small lymph nodes $< 2\text{ cm}$, an increase of $< 25\%$ is not considered to be significant.

^c. This parameter is not relevant for the PD category.

^d. Subjects with treatment-related lymphocytosis should remain on study treatment in the absence of other criteria for progressive disease.

¹. Group A defines the tumor load and Group B defines the function of the hematopoietic system

². CR: all of the criteria need to be met and patients have to lack disease-related constitutional symptoms. Bone marrow aspirate at least 2 months following the last dose of nivolumab is required to confirm CR.

³. PR: At least 2 criteria from Group A plus 1 of the criteria from Group B must be met. In all cases, in order for a response to be termed a PR, the blood lymphocyte count should be normalized or decreased $> 50\%$ from baseline (if elevated at baseline).

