7.5.5. Biomarker Data Analysis Methods for PDL1, and NGS and GEP (if available)

- Median, mean (SD), and range for continuous variable or N and frequency (%) for categorical variables will be reported for all-treated versus the biomarker populations for selected demographic and baseline characteristic variables including the biomarker stratification cohorts.
- The number of subjects (N) and the associated percentage (%) will be presented to facilitate the evaluation of the response rate. The median duration of response (arising from Kaplan-Meier estimate) between 1) PDL1 IHC option 1/2 subgroups (i.e., not elevated/negative vs. elevated/positive); 2) NGS subgroups (i.e., negative vs. positive); 3) GEP subgroups (i.e., >median vs. <=median) will also be reported.

The relationship between 1) PDL1 not elevated (or negative) vs. elevated (or positive) subgroups; 2) NGS negative vs. positive subgroups; 3) GEP subgroups >median vs. <=median subgroup for duration of response, progression-free survival and overall survival will be evaluated by the Kaplan-Meier method. If the number of subjects is ≤ 7 then Kaplan-Meier analyses are unnecessary.

- For each of the biomarker stratification cohort, Fisher exact test will be used to test the association on the response between 1) PDL1 subgroups (not elevated and elevated for option 1; negative and positive for option 2); 2) NGS subgroups (negative vs. positive); 3) GEP subgroups (>median vs. <=median)
- Descriptive summary statistics [i.e., mean (SD), median and range] will be used to evaluate time to initial response and best response of the PDL1, NGS and GEP subgroups for each of the biomarker stratification cohort.

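### The SAP's best-response ranking puts nodular PR below ordinary PR, against the protocol's own definition; this affects only descriptive and exploratory best-response outputs in CLL

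*SAP*

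**What the plan says.** SAP section 2.7 (Other General Definitions) lists the response categories with ranks: CR 1, CRI 2, PR 3, NPR 4, PRL 5, then SD, PD and the non-evaluable codes. The selection rule is "The response corresponds to the lowest rank of number is the best response". The date of best response is the date on which that category is first observed. The SAP's example shows the purpose: "for subjects who achieved PR followed by CR, PR will be the initial response and CR will be the best response", with the later CR date used.

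Protocol Attachment 6.1 (IWCLL) says of nodular PR: "nPR is a response where subjects meet the criteria for a CR, but the bone marrow biopsy shows that there are still B-lymphoid nodules" present. It adds: "These nodules are residual disease and therefore the subject is termed an nPR". For ordinary PR, the footnote reads "PR: At least 2 criteria from Group A plus 1 of the criteria from Group B must be met", with a further condition on the blood lymphocyte count if it was elevated at baseline. The stable-disease row of the same table names nPR after CRi and before PR.

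Best response, or its date, is used in four places:
- the Part A listing of individual best tumor responses (Protocol section 12.4);
- the summary of best response in subjects whose lymphoma symptoms resolved (SAP section 4.3.4);
- the list of biomarker endpoints (SAP section 7.5);
- the PD-L1, NGS and GEP subgroup summaries, where descriptive statistics "will be used to evaluate time to initial response and best response" (SAP section 7.5.5).

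**The concern.** A best-response ranking should run from deepest to shallowest. The SAP's list does so elsewhere: CRI sits below CR, and PRL below PR. The exception is PR and NPR, where the category that falls short of CR only by marrow nodules is ranked below one that can be met with partial reductions.

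What is at stake is the reported depth of response among CLL responders and the time at which the best response is said to have been reached. A subject who deepens from PR to NPR is shown as not having deepened. A subject who goes from NPR to PR is shown as reaching best response at the later, shallower assessment.

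**Working it through.** The plan states no figure here, so there is nothing numerical to reproduce. The check has three steps.

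**1. Compare the definitions in Attachment 6.1.**
- CR requires every Group A and Group B criterion and no disease-related constitutional symptoms.
- nPR requires the CR criteria, with residual nodules on the marrow biopsy as the only shortfall.
- PR requires two Group A criteria plus one Group B criterion, and the lymphocyte condition. Its Group A thresholds are reductions of about half, where CR requires no hepatomegaly, no splenomegaly and no node above 1.5 cm. Its Group B thresholds are the same absolute values as for CR, or alternatively a 50% improvement over baseline.

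On these definitions nPR is the deeper response. Neither document gives a reason for ranking it lower.

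**2. Apply the SAP rule.** Best response is the category with the smallest rank among those recorded, and its date is the first occurrence of that category. The sequences and week numbers below are illustrative assumptions; the alternative ranking places NPR at 3 and PR at 4.

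| Recorded sequence (week) | SAP ranking | NPR above PR | First response |
|---|---|---|---|
| PR (10), NPR (20) | PR, week 10 | NPR, week 20 | week 10 |
| PRL (10), PR (20), NPR (30) | PR, week 20 | NPR, week 30 | week 10 |
| NPR (10), PR (20) | PR, week 20 | NPR, week 10 | week 10 |
| PR (10), NPR (20), CR (30) | CR, week 30 | CR, week 30 | week 10 |
| SD (10), NPR (20) | NPR, week 20 | NPR, week 20 | week 20 |

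The result differs only when PR and NPR are both recorded and neither CR nor CRi is. The date is too early if PR came first and too late if NPR came first.

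**3. Trace the consequence.**
- *ORR* (SAP section 4.2.1) counts PR(+L) or better. Ranks 1 to 5 all qualify under either order, so the response count is the same.
- *Date of first response and DOR* (SAP sections 2.7 and 4.3.1) start at the first PR(+L) or better. The last column of the table is the same under both rankings.
- *PFS, OS and duration of stable disease* (SAP sections 4.3.2 and 4.3.3) do not use the rank.
- *Population*: SAP section 4.1.3 applies IWCLL to CLL only. The Lugano criteria used for SLL, FL, DLBCL and Richter syndrome have no nPR category.

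**The case against.** The strongest argument for the SAP is that Attachment 6.1 describes nPR inside the Partial Response row, so nPR is a kind of PR and the order hardly matters. That would justify pooling the two. It does not justify separate ranks with the deeper category lower, which is what the SAP specifies.

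The objections to the size of the problem largely stand. A reader might infer four stronger things that the documents do not support:

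- *That nPR would almost never be reported, or that the error is systematic along the clinical path to nPR.* Nodular PR needs a marrow biopsy. Table 1 of the protocol accepts aspirate or biopsy for the repeat marrow, asks for it once, only in subjects with marrow involvement before treatment, and stops it after clinical cutoff. NPR may rarely be recorded at all. The repeat marrow is preferably done within 30 days of first documenting CR. If that visit is first coded CR pending the marrow result, and stays so coded, the rule returns CR under either ranking. The documents do not say how such a visit is coded.
- *That the date is wrong by at least one scan interval.* Attachment 5 gives scheduled spacings of about 10 and later 24 weeks. Unscheduled assessments are possible, so these are not lower bounds.
- *That the main CLL efficacy results are affected.* They are not. The SAP has no depth-of-response efficacy endpoint; best response enters only listings and exploratory summaries.
- *That the information is lost.* SAP section 4.2.2 provides a listing of tumor response by assessment visit, in which any recorded NPR remains visible.

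**Conclusion.** The ranking is wrong as written. It conflicts with the definition in Attachment 6.1 and with the deepening logic of the SAP's own example. The conclusion is conditional: for an IWCLL-assessed CLL subject in Part A or Cohort B1 with both PR and NPR recorded and no CR or CRi, best response is always reported as PR at the date of the first PR, irrespective of order.

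The consequence is small. It is confined to a category label and its date in descriptive or exploratory outputs. The number of such subjects cannot be derived from the documents and may be small. The conclusion rests on the two categories being recorded separately at assessment, as the SAP's separate ranks imply, and on the ranking being programmed as printed.

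**What to change.** In SAP section 2.7, rank CR 1, CRI 2, NPR 3, PR 4, PRL 5 and leave the remaining codes as they are. Then re-derive best response and date of best response for IWCLL-assessed CLL subjects from the existing data, and refresh the Part A best-response listing, the symptom-resolution summary and the biomarker best-response and time-to-best-response summaries.

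The cost is a one-line SAP change, the matching programming change, and a rerun of those outputs. No new data are needed and no primary or time-to-event analysis has to be repeated. If the team prefers to treat nodular PR as part of PR, the coherent alternative is to pool NPR and PR under one rank and state the reason, accepting that the depth distinction is then not reported.
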